Aim 3: Explore the intended effects of taVNS in people with neuropathic pain. The sample consent form and brochure for taVNS will not specify the exact location on the ear for active taVNS. Thus, participants in the TMS video only group will be sufficiently naïve for participation in a single blinded crossover design. Half of the TMS-only group will receive active taVNS in visit 2, the other half will receive sham taVNS in visit 2, and they will crossover for visit 3 (table 1). *We hypothesize that there will be a greater increase in HRV and SICI with active taVNS than with sham taVNS.*

4) Background*

Noninvasive neurostimulation techniques show promise for improving chronic pain management.¹⁻³ Underrepresented racial minorities (URM) are at greater risk than non-minority individuals for persistent pain conditions⁴⁻⁶; however, recruiting URM for adequate representation in neurostimulation research remains an unmet challenge. Improving recruitment of URM participants in neurostimulation research

is critical to enhancing our understanding of factors that influence outcomes with these modalities and to maximize the generalizability of research findings to a diverse population.

Traditional consent forms have been criticized for being too long and difficult to understand, and these consent forms may be a barrier to URM participation in research, as limited literacy disproportionately affects URM and the text heavy format may foster distrust. Video-enhanced informed consent (VE-IC) has been recommended to improve recruitment of URM in cancer and cardiovascular trials; however, VE-IC has not been studied in neuromodulation research.

5) **Inclusion and Exclusion Criteria***

We anticipate that most participants in this study will have chronic pain associated with chemotherapy induced peripheral neuropathy (CIPN); however, we will recruit Black and Hispanic people with chronic neuropathic pain of any etiology (e.g., diabetic neuropathy and radiculopathy) to optimize the rapid recruitment of these URM.

Inclusion Criteria: 1) between the ages of 18-80 years; 2) neuropathic pain lasting longer than 3 months (i.e., complaint of sensation of burning, stabbing or pressing pain, shooting or shock like pain, or paresthesias); 3) Neuropathic Pain Symptom Inventory score ≥ 10 . 4) self identifies as Black or Hispanic

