Exclusion Criteria: 1) any unstable medical condition or medical contraindication to moderate physical exertion (e.g., unstable angina or cardiac arrhythmia), 2) pregnancy, 3) currently taking Buprenorphine or recently stopped taking (within 1 month), 4) presence of cognitive impairment or language barrier that impairs full autonomy in the consent process or in the ability to participate in detailed interviews, 5) implants in the head or neck, cochlear implants, or pacemaker, 6) head or neck metastasis or recent ear trauma, 7) history of seizures.

6) **Study-Wide Recruitment Methods***

All recruitment will be in accordance with the Health Insurance Portability and Accountability Act (HIPAA), by the SCCC Protocol Review and Monitoring Committee and by the UM Department of Physical Therapy Research Leadership Team.

Black and Hispanic patients with persistent pain will be recruited for a 2-phased mixed methods study. Flyers will be placed in Uhealth clinics (Uhealth Physical Therapy, Uhealth Advanced Pain Management Center, and Sylvester Comprehensive Cancer Center) to recruit patients with neuropathic pain. In addition, the patient census of specific UHealth clinics (i.e., [name] medical oncology clinic, the Sylvester Posner Lymphema Clinic, and the Uhealth Pain Physical Therapy Clinic) will be used for recruitment. *Physicians will be informing participants first about the study before a member of the study team will be contacting patients.* Telephone numbers and/or emails of potential participants and they will be called to screen for inclusion. Patients who provide verbal consent to be

contacted for research purposes will be called by one of the research assistants.

The Sylvester Behavioral and Community-Based Research (BCSR) Shared Resource will be used to assist with recruitment of patients with chemotherapy induced peripheral neuropathy (CIPN).

7) Study Design

Primary Purpose: Other. This study will utilize principles of community-based participatory research to develop and test educational materials for consenting people to neurostimulation research.

Study Phase: N/A

Interventional Study Model: Parallel

Number of Arms: 2

Masking: Subject only

Allocation: Randomized

Enrollment: 28

8) Study Timelines*

Each participant will complete 3 visits for a total of ~10 hours, and it is expected that the visits are completed within 1-2 weeks of each other. Thus, participants will be enrolled for less than 3 weeks on average.

9) Study Endpoints*

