Primary Outcome Measure Title: Change in Heart Rate Variability (HRV)

Primary Outcome Measure Description: HRV will be measured with an H10 chest strap device (Polar, Finland)

Primary Outcome Measure Timeframe: at visits 2 and 3, Baseline (15 minutes pre taVNS application) to 15 minutes post 1 hour application of taVNS

Secondary Outcome Measure Title: Change in EXPECT questionnaire scores

Secondary Outcome Measure Description: scores ranging from 0-40 with higher scores representing greater expectations for pain relief

Secondary Outcome Measure Timeframe: at visits 2 and 3, Baseline (pre taVNS application) and repeated post 1 hour application of taVNS

10) Arms and Interventions

All participants will be educated on both neurostimulation modalities (taVNS and TMS). This study will include 2 arms. Group 1 will receive a supplemental video on taVNS, in addition to consent forms and brochures describing both modalities.

Group 2 will only receive the consent forms and brochures describing both modalities. While all participants will provide important feedback on consent forms and brochures for both modalities, Group 1 will provide additional feedback specific to the taVNS video they watched.

We will assess the impact of the taVNS video (by comparing Group 1 to Group 2) on participant expectations and intended effects with a single 60-minute bout of taVNS.

11) Procedures Involved*

Black and Hispanic patients with persistent pain will be recruited for a 2-phased mixed methods study. All data collection will take place at the Lynn Rehabilitation Center. In the first phase, participants will be educated on two neurostimulation modalities (taVNS and TMS).

Educational materials will include 1:1 discussion of a typical consent form for each modality, a brief (2 page) description with pictures for each modality, and the brief video for taVNS for those randomly allocated to Group 1. *The development of these educational resources is a primary objective of this project, and the first few months will be spent consulting with experts to develop these educational resources and to produce the videos.*

Structured interviews and questionnaires will be used to examine participants interest in participating in research for each of the modalities, gather their feedback on each educational tool, and to determine factors that influence their interest. This first phase will take place in a single session, and the session is anticipated to take ~2 hours to complete.

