Participants will be given the choice to complete this first visit in person or via Zoom in order to decrease participation burden. For the second phase, all participants will receive active taVNS, but only Group 2 will receive both active and sham taVNS in a randomized crossover design.

All participants will first complete a pretrial assessment battery, followed by a 60-minute trial of taVNS applied with continuous monitoring of HRV during quiet sitting, and then concluded with a posttrial assessment. The second phase will be completed in two sessions that are anticipated to last ~4 hours each. In summary, participants will complete 3 visits for a total of ~10 hours to complete the study.

	Visit 1	Visit 2	Visit 3
taVNS video (n=12)	Education and baseline	Active taVNS	1-wk follow up
Brochures only (n=12) 6 participants	Education and baseline	Active taVNS	Sham taVNS
6 participants	Education and baseline	Sham taVNS	Active taVNS

A detailed description of each procedure is provided below:

*EXPECT questionnaire*⁷: The EXPECT is a 4-item questionnaire that assesses expectations for pain improvement. Each of the 4 items is scored on an 11-point scale, with 0 being no change and 10 representing complete relief. It is anticipated that this questionnaire will take less than 5 minutes to complete.

Heart rate variability (HRV): HRV will be measured with an H10 chest strap device (Polar, Finland) and will serve as the primary endpoint for response to taVNS in Aim 2. Participants will wear the chest strap continuously throughout the application of taVNS.

taVNS: A portable taVNS Stimulator (Soterix Medical, Woodbridge, NJ) will be used with flexible hydrogel electrodes to administer taVNS at the cymba concha (Figure 2), using monophasic pulses (pulse width:500 μ s; frequency 10 Hz), and delivered up to 200% of the perception threshold, but kept below the pain threshold, for 60 minutes. This device is approved for research purposes, and these parameters have been shown to maximize cardiovagal response with taVNS.⁸ Participants will be quiet sitting in a comfortable chair during the application of taVNS.

Figure 2. taVNS electrode application

Please see the Risks to Subjects section for procedures performed to lessen the probability or magnitude of risks.

12) Data Management*

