The principal investigator will be responsible for all data management and analyses. A research assistant will assist with data entry and qualitative data coding. All quantitative data will be entered and stored in the University of Miami REDCap system. NVivo 12 software (QSR International, United States) will be used for qualitative data management and analyses, and SPSS version 28 (IBM, United States) will be used for quantitative analyses (i.e., descriptive statistics).

13) Provisions to Monitor the Data to Ensure the Safety of Subjects*

Safety information will be collected during the taVNS trial study visit for this research and entered into Velos for tracking. All adverse effects will be reported to the study team, the IRB, and to the SCCC Data & Safety Monitoring Committee. All research activities will be stopped in the case

of a single serious adverse reaction (i.e., seizure) or if 3 or more minor adverse reactions (e.g., skin irritation from electrodes) are observed. A corrective plan (e.g. change in TMS or taVNS protocol) must be approved by the study team, IRB, and SCCC Data & Safety Monitoring Committee before research activities can be resumed.

The plan might include establishing a data monitoring committee and a plan for reporting data monitoring committee findings to the IRB and the sponsor.

14) Community-Based Participatory Research*

Prior to initiating research activities, a 4-member community advisory board (CAB) will be assembled, consisting of 2 people from each ethnicity (non-Hispanic African American and Hispanic), and the CAB will meet 4 times over the course of the year to provide general feedback on the project design, plan, and progress, including feedback on video scripts, final video products, and video dissemination plan. At least 1 person from each ethnic group on the CAB must have chronic pain (n≥2).

15) Sharing of Results with Subjects*

NA

16) Setting

Participants will be recruited from Sylvester Comprehensive Cancer Center, UHealth Physical Therapy, and from the UHealth Advanced Pain Management Clinic.

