19) Confidentiality

Confidentiality will be maintained by assigning participant identification numbers at the beginning of the study. All data will be identified using these ID numbers. The personal information included as data will consist of the gender, age, race, ethnicity, and cancer type and treatment. This information will be kept in a locked file cabinet and stored in a password-protected digital file on the encrypted database at the University of Miami Physical Therapy Department located at [name]. Signed consent forms will be kept in a master file in a locked file cabinet. Only the principal investigator and research assistant will have access to participant's personal information and data.

20) Provisions to Protect the Privacy Interests of Subjects

Participants will only interact directly with their respective Uhealth providers for recruitment (i.e., a Uhealth provider who already has access to the patient census would contact the patient for study recruitment, and the data collection will be

performed by investigators who are members of the Uhealth clinical team). Thus, the intrusiveness of participation is minimized.

Only IRB approved research team members will have access to study records. Overall study results will not be shared with study participants, individually. Confidentiality will be maintained by assigning subject identification numbers at the beginning of the study. All data will be identified using these ID numbers. This information will be kept in a locked file cabinet and stored in a password-protected digital file on the encrypted database in the office of the PI in the University of Miami Department of Physical Therapy located at [name]. Signed consent forms will be kept in a master file in a locked file cabinet. Only the principal investigator and research assistant will have access to subject's personal information and data.

21) Compensation for Research-Related Injury

Compensation will not be provided for research-related injury. Funds to compensate participants for pain, expenses, lost wages, and other damages caused by injury are not available. However, treatment will be available in most cases and their insurance may be billed or participants will have to pay.

22) Economic Burden to Subjects

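### HRV processing is not masked to arm or to active/sham condition, although coding the recordings would be a cheap safeguard

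*Combined protocol and SAP*

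**What the plan says.** **Masking.** Section 7 (Study Design) gives "Masking: Subject only". Aim 3 in section 3 describes the participants in the active/sham comparison as "sufficiently naïve for participation in a single blinded crossover design". Neither place masks an investigator, assessor or analyst.

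**Roles.** Section 12 (Data Management) says "The principal investigator will be responsible for all data management and analyses", and then "A research assistant will assist with data entry and qualitative data coding". It describes the quantitative analysis only as descriptive statistics in SPSS.

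**Endpoint.** Change in HRV is the primary outcome in section 9. It is recorded by a chest strap, from 15 minutes before stimulation to 15 minutes after the one-hour application. Section 11 adds that HRV "will serve as the primary endpoint for response to taVNS in Aim 2". Aim 2 compares people who did and did not see the taVNS video. Aims 2 and 3 both state directional hypotheses for HRV.

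**Existing coding.** Section 19 (Confidentiality) says "All data will be identified using these ID numbers" and also "Only the principal investigator and research assistant will have access to participant's personal information and data".

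**The concern.** A chest strap yields a beat-to-beat signal. Turning that into one HRV value per time point involves choosing an index, dealing with irregular or missed beats, fixing the exact window, and deciding whether a poor recording is kept. The protocol names the device and the time frame. It does not name an index, an artefact rule, processing software or an exclusion rule.

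If whoever makes these choices knows the arm or the condition, and the study has a stated direction of effect, the choices can drift towards the hypothesis without any intent. With 12 participants per group in the visit table of section 11, one recording is 1/12, about 8%, of a group or of the crossover pairs, so a few judgements carry weight.

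**Working it through.** **1. Is any stage after recording masked?**

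- Section 7 masks participants only, and Aim 3 is single-blind.
- Section 12 gives the principal investigator responsibility for all data management and analyses. The research assistant's stated help is with data entry and qualitative coding.
- Section 19 attaches ID numbers to data, but the principal investigator has access to both the personal information and the data. An ID does not hide allocation.
- The visit pattern in section 11 can reveal the arm: the video group has active taVNS at visit 2 and a one-week follow-up at visit 3, while the brochures-only group has a stimulation session at both.
- No available section describes coded condition labels, masked processing, or values locked before unmasking.

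**2. Which comparison is affected, and by what knowledge?**

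- Aim 2 (video v no video, parallel groups) is where section 11 places HRV as primary endpoint. Aim 2 concerns the response to active stimulation in both groups, so the relevant knowledge is the arm.
- Aim 3 (active v sham within the brochures-only group) is introduced as exploratory. Here the relevant knowledge is the condition of each session.

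**3. How large could it be?** The documents give no SD, effect size, alpha or test for HRV, so there is no figure to reproduce. What follows is illustrative. The group size of 12 comes from section 11. The shifts and the two-sided 5% t-test are my assumptions. The SD is that of the change in HRV for Aim 2 and of the active-minus-sham difference for Aim 3.

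*Shift in a mean.* If 3 of 12 values move by 0.5 SD in the expected direction: 3/12 × 0.5 = 0.125 SD.

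*95% confidence interval half-widths.*
- 12 v 12: t(0.975, 22 df) × √(2/12) = 2.074 × 0.408 = 0.85 SD; 0.125/0.85 ≈ 15%.
- 12 pairs: t(0.975, 11 df)/√12 = 2.201/3.464 = 0.64 SD; 0.125/0.64 ≈ 20%.

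*False-positive rate with no true effect.* If processing adds a shift of b SD to the comparison, the t statistic is noncentral with parameter b√6 (12 v 12, 22 df) or b√12 (12 pairs, 11 df). The rejection rates are:

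| Assumed shift b | 12 v 12 | 12 pairs |
|---|---|---|
| 0 | 5.0% | 5.0% |
| 0.125 SD | 6.0% | 6.8% |
| 0.2 SD | 7.6% | 9.7% |
| 0.3 SD | 10.8% | 15.8% |
| 0.5 SD | 21.6% | 35.3% |

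The 3-of-12 scenario therefore has a modest effect. The rate climbs quickly only if the average shift over all recordings is larger.

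**The case against.** **The outcome is recorded by a device, in an openly single-blind study.** The raw signal is indeed objective, and section 9 fixes the broad time frame, which leaves less room for window choice than an open-ended recording would. The analysed value still depends on an index and on artefact handling, and the text leaves both open. Prespecifying them would remove much of the discretion. It would not remove case-by-case judgement on poor recordings.

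**A reader might infer that the principal investigator personally edits the HRV files knowing which session was active.** The documents do not say so. Section 12 assigns responsibility; it does not describe who processes HRV, with what software, or whether any manual editing takes place. Part of the text following the start of section 17, where staff roles may be described, was not available for this review. What stands is narrower: no available section masks the processing, whoever does it.

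**A reader might also take the active/sham contrast, and hence the 20% figure, as the effect on the primary comparison.** Section 11 ties the primary HRV endpoint to Aim 2, a parallel comparison, for which the same assumed shift is about 15% of the half-width. The 20% belongs to the exploratory crossover.

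**The magnitude is assumed, and no test or interval is planned in the available text.** This is correct. The figures show sensitivity at this sample size; they are not an estimate of bias in this trial.

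**Coding takes more than renaming files.** This also stands. Pre and post recordings must stay linked so that change can be calculated, and the code must be independent of existing IDs and dates.

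**Conclusion.** The point holds as a low-severity improvement. As written, the plan leaves HRV processing open to knowledge of arm (Aim 2) and of condition (Aim 3), with no index or artefact rule to constrain it and no masking after the recording is made.

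The documents do not show that any bias will occur, and its size cannot be derived from them. Over assumed shifts of 0.2 to 0.5 SD, the two-sided 5% error rate would become about 8–22% for 12 v 12 and 10–35% for 12 pairs. Under the milder 3-of-12 scenario it would be 6.0% and 6.8%.

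It would go too far to say that coded files would prevent knowledge of allocation from influencing the endpoint. They protect processing and analysis. Staff running the sessions remain unmasked under the declared design.

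**What to change.** Add to section 12:

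- The existing research assistant gives each session's linked pre/post HRV recordings a random code that is independent of participant ID, removes dates and any other label that reveals arm, visit or condition, and holds the key.
- Whoever processes the recordings completes artefact correction, window selection and exclusions on the coded files, then locks the values.
- The code is broken only after the analysis script is fixed.

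If the research assistant would process the recordings, another team member should hold the key. Naming the HRV index and the artefact rule in the same section would complement the coding. If a masked-processing safeguard already exists, stating it in section 12 would settle the point.

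**Cost.** By the visit table there are 12 × 1 + 12 × 2 = 36 stimulation sessions to code. Processing is slightly slower and a key has to be maintained. Sample size, visits and stimulation are unchanged, and no new staff appear to be needed. That the cost is small is a judgement, but a reasonable one for a study of this size. The step can also be applied to stored recordings that have not yet been processed.

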TITLE PAGE

Full protocol title: Addressing Disparities in Neuromodulation for Rehabilitation: A Mixed Methods Approach to Optimize Access for Underrepresented Racial Minorities

Protocol Version Date: **12/16/2023**

PI Name: **[name]**

NCT Number: NCT05896202

1) Protocol Title

Addressing Disparities in Neuromodulation for Rehabilitation: A Mixed Methods Approach to Optimize Access for Underrepresented Racial Minorities

2) IRB Review History*

Approved (ID 20230154)

3) Objectives*

We will develop culturally sensitive videos for video-enhanced informed consent (VE-IC) with neuromodulation techniques (i.e., vagus nerve [taVNS] and transcranial magnetic [rTMS] stimulation techniques). We will use these videos in a mixed method study design to examine factors that influence the interest or aversion to participate in neurostimulation research in URM with persistent pain. Findings will provide insight on modifiable factors and recruitment/retention strategies to optimize racial minority representation in neurostimulation research. The videos and data from this project will be used in our future research on neurostimulation, and they will be made available for use by others. This study is part of a larger research agenda designed to inform the development of personalized pain relief programs based on using patient preferences and a mechanistic understanding of the interventions to integrate neurostimulation interventions into multimodal care for persistent pain.

Aim 1: Development of culturally sensitive videos for enhance informed consent with neurostimulation and determination of factors that influence minority interest in participating in neurostimulation research. *We hypothesize that participants will have greater interest in participation and expectations for pain relief with the modality for which they received VE-IC in comparison to modalities without VE-IC.*

Aim 2: Examination of the influence that video enhanced informed consent has on expectations with taVNS and on treatment intended effects. *We hypothesize that individuals who had VE-IC for taVNS will demonstrate greater expectations for pain relief and greater changes in heart rate variability (HRV).*

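### The plan specifies only descriptive statistics, with no within-person active-minus-sham estimate and no interval, and its EXPECT change endpoint removes any video effect already present

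*Combined protocol and SAP*

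**What the plan says.** - Section 12 (Data Management), on the quantitative analysis: "SPSS version 28 (IBM, United States) will be used for quantitative analyses (i.e., descriptive statistics". The abbreviation makes this a definition, not an example. The same section makes the principal investigator responsible for all analyses.
- Section 3, Aim 2, hypothesises that "individuals who had VE-IC for taVNS will demonstrate greater expectations for pain relief and greater changes in heart rate variability (HRV".
- Section 3, Aim 3: "We hypothesize that there will be a greater increase in HRV and SICI with active taVNS than with sham taVNS".
- Section 10: "We will assess the impact of the taVNS video (by comparing Group 1 to Group 2) on participant expectations and intended effects".
- Section 11 places a randomised active/sham crossover in Group 2. Its table has 12 people in the video group, all with active taVNS at visit 2, and 12 in the brochures-only group. Six of those 12 have active then sham, and six have sham then active.
- Section 9: "Primary Outcome Measure Title: Change in Heart Rate Variability (HRV", with a device and the window "Baseline (15 minutes pre taVNS application) to 15 minutes post 1 hour application of taVNS". No HRV index is given. The EXPECT time frame is "at visits 2 and 3, Baseline (pre taVNS application) and repeated post 1 hour application of taVNS".
- Section 7: "Masking: Subject only".

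The text between sections 17 and 19 was not available for review. Nothing elsewhere points to a statistical section there.

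**The concern.** The design is comparative and the analysis text is not. A sham session given to the same people has little purpose without an active-minus-sham contrast. If the report gives only means, SDs and n by condition, a reader can rebuild an unpaired interval. The paired interval cannot be rebuilt, because it needs the SD of the within-person differences.

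The EXPECT endpoint has a separate problem of timing. Aim 2 asks whether the video raises expectations. The video belongs to visit 1, but the change score starts at visit 2, so an effect that is already there is subtracted out.

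Two further details are open. No HRV index is fixed for the primary outcome. Nor does the plan say whether Aim 2 uses Group 2's active sessions at visit 2, at visit 3 (after sham), or both. Only participants are masked, so either choice could be made with condition known.

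**Working it through.** **Inputs.** Group sizes are from the section 11 table (12; 6; 6). The protocol gives no alpha, SD, correlation, effect size or power, so it has no precision figure of its own to reproduce. I assume two-sided 95% intervals, an SD of 1 for each outcome, and a between-session correlation ρ of 0.3, 0.5 or 0.7 for HRV change.

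**Aim 3, active minus sham, 12 people.**
- Unpaired half-width: t(22) × √(2/12) = 2.074 × 0.408 = 0.85.
- Paired, adjusted for period: t(10) × √(2(1−ρ)/12), with t(10) = 2.228. This gives 0.76, 0.64 and 0.50 at ρ = 0.3, 0.5 and 0.7.
- Break-even: ρ = 1 − (2.074/2.228)² = 0.13. At ρ = 0 the paired half-width is 0.91.
- Matching the paired half-width without pairing would take 15, 20 or 33 per condition. These are the smallest n for which t(2n−2) × √(2/n) is no larger than the paired value.
- Carryover: if carryover into the later active session exceeds that into the later sham session by x, the estimate shifts by 0.5x, because each sequence supplies half of it.

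**Aim 2, HRV change.** Group 1 has stimulation only at visit 2.
- Visit 2 only, 12 v 6: t(16) × √(1/12 + 1/6) = 2.120 × 0.500 = 1.06. This needs no carryover assumption.
- Joint model of Group 1 visit 2 and all Group 2 sessions, with terms for group, stimulation and visit. The Group 2 active, visit 2 mean is estimated with weights 0.75 and −0.25 on the active and sham sessions of the active-first sequence, and 0.25 and 0.25 on the two sessions of the sham-first sequence. So SE² = 1/12 + (0.75 − 0.25ρ)/6, and SE = 0.4425, 0.4330 and 0.4233. With t(21) = 2.080 the half-widths are 0.92, 0.90 and 0.88.
- Cost of that gain: an effect d of prior sham on the later active session shifts the group estimate by −0.25d. The two options have equal mean squared error at d = √(0.25 − SE²)/0.25 = 0.93, 1.00 and 1.06 SD.

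**Aim 2, EXPECT.** Suppose the video raises visit 2 pre-taVNS EXPECT by δ and a fraction f of this remains afterwards. Apart from any effect of the stimulation itself:
- Between-group contrast in change: fδ − δ = (f − 1)δ. This is 0 at f = 1 and −0.5δ at f = 0.5, so a lasting benefit appears as nothing and a fading one as harm.
- Between-group contrast in the pre-taVNS score: δ, with half-width t(22) × √(2/12) = 0.85 SD of that score (12 v 12).

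**Sensitivity to sample size.** Section 7 states an enrolment of 28, but the table totals 12 + 6 + 6 = 24, and the text does not reconcile them. If 28 were split 14/7/7 (an assumption), the half-widths would be 0.78 for two groups, 0.97 for visit 2 only, and 0.69, 0.58 and 0.45 paired.

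**The case against.** The strongest reply is that this is a small mixed-methods study. Developing educational material is one of its main purposes, Aim 3 is worded as exploration, and descriptive reporting is defensible. That stands as a reason to label results exploratory. It does not explain why directional hypotheses and a randomised crossover come with no stated contrast, and bare means from 12 or 6 people are easier to over-read than wide intervals.

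A reader might infer several stronger things that the protocol does not support:
- *The plan rules out a within-person estimate, or the crossover's precision is lost.* A mean paired difference is itself a descriptive statistic, and the paired data will be collected. The estimate is unspecified, not excluded.
- *No interval is planned because no HRV index is named.* These are separate gaps.
- *The index or session will be chosen to suit the result.* The documents show only that the opportunity exists.
- *Visit 2 only is the right Aim 2 analysis.* It leaves out six people's active sessions, and section 9 sets the outcome at both visits. The joint model has the lower mean squared error unless a prior-sham effect exceeds about 0.9 to 1.1 SD. Either is defensible.
- *A sequence term makes the joint model equivalent to visit 2 only.* That depends on coding. With active-first as reference the SE is 0.500 and the shift is 0; with sham-first as reference the SE is 0.500 and the shift is −0.50d; centred coding changes neither the SE nor the −0.25d shift.

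It is also fair to say that this point does not choose the HRV index and offers no analysis for SICI, which Aim 3 names but sections 9 and 11 do not describe.

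**Conclusion.** The point holds in this form. Section 12 limits the quantitative analysis to descriptive statistics and specifies neither a within-person active-minus-sham estimate nor an interval for any comparison. The EXPECT change score cannot by itself answer the expectations part of Aim 2, because it removes any video effect already present at visit 2. The unnamed HRV index and the unidentified Group 2 session are separate gaps of detail.

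Pairing would narrow the Aim 3 interval by 0.09, 0.20 or 0.35 SD (0.85 less 0.76, 0.64 or 0.50). These sizes rest on assumed correlations and on the table's 24 participants; using 28 would not change the conclusion. Under any of the options only large effects could be separated from zero. The EXPECT argument needs no numerical assumption beyond the visit order: a between-group contrast in change cannot contain a difference that is the same before and after.

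**What to change.** Replace the parenthesis in section 12 with a short analysis paragraph:

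1. **Aim 3.** In Group 2, the within-person active-minus-sham difference in pre-to-post HRV change, adjusted for period, with a 95% CI and a statement that it assumes no differential carryover.
2. **Aim 2, expectations.** Keep the change endpoint. Add the between-group difference in visit 2 pre-taVNS EXPECT, with a 95% CI, as the estimate of the video's effect.
3. **Aim 2, HRV.** State in advance which Group 2 active sessions are used, and report the group difference with a 95% CI. Use either visit 2 only (12 v 6, no carryover assumption) or a joint model of all sessions (more precise, assumes no carryover).
4. **HRV index.** Fix one primary index before any data are examined, computed on the stated 15-minute windows; treat the others as exploratory.
5. Label all results exploratory, and reconcile the enrolment of 28 with the table's 24.

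The cost is a paragraph of text and one added EXPECT contrast. No visit, participant or measurement is added, since pre-taVNS EXPECT at visit 2 is already planned. Pairing loses slightly if the between-session correlation is below 0.13. Choosing visit 2 only for Aim 2 HRV widens the half-width from about 0.9 to 1.06 SD; choosing the joint model means relying on the carryover assumption.
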